#### 10.4.3 ANALYSIS OF THE SECONDARY ENDPOINT(S)

##### **#2 (Secondary): Quantify the impact of Shade on the numbers of new AK's observed at the final visit**

This analysis will follow the same procedure as the primary analysis but will only include AK data from the final visit.

##### **#3 (Secondary): Quantify the impact of Shade on the numbers of new cutaneous squamous cell carcinomas confirmed by histology during follow up over the study period.**

To test the early effect of Shade on skin cancer risk and the robustness of our findings, we will perform a longitudinal analysis to test a reduction by at least 25% of squamous cell carcinoma. The effect of Shade use will be estimated using a single mixed linear model (with random intercept and slope) for repeated (longitudinal) data including study group and time since enrollment as explanatory variables. A similar stepwise multivariate approach with backward selection as described in the primary aim will be performed to take into account confounding factors.

**#4 (Secondary): Quantify the impact of Shade on the number of new nonmelanoma skin cancers (basal cell carcinomas, cutaneous squamous cell carcinomas) confirmed by histology over the study period.**

To test the early effect of Shade on skin cancer risk and the robustness of our findings, we will compare the cumulative numbers of new nonmelanoma skin cancers between the control and study group and test a reduction by at least 25% of non-melanoma skin cancer s as secondary outcome, using a t-test. A similar stepwise multivariate approach with backward selection as described in the primary aim will be perform to take into account confounding factors.

**#5 (Secondary): Test the correlation between measured UV exposure and the number of new actinic keratoses.**

We will test the correlation between the cumulative UV exposure and the number of AK lesions at each time point using a Pearson correlation test or a non-parametric Spearman test if the requirements for the parametric test are not met. A significant correlation will be defined as  $p > 0.2$  and  $p\text{-value} < 0.05$ . UV exposure will be defined as the cumulative UV exposure in erythemally-weighted  $\text{J/m}^2$  at each time point since enrollment.

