control group will not wear a sensor. This choice of control group allows us to provide standard of care advice to these subjects. The behavior change in the treatment group is expected to be a result of both the decision to engage with the device, for example by putting it on and opening the App as well as due to the knowledge of personal UV exposure reported by the device. We expect to gather information on the cumulative UV exposure of all subjects by using an ELISA assay for cyclopyridimine dimers (CPD) from photoexposed skin.

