## 4 STUDY DESIGN AND ENDPOINTS

### 4.1 DESCRIPTION OF THE STUDY DESIGN

This randomized partially blinded study will recruit 120 patients with a history of actinic keratosis (AK) lesions. A control versus study group analysis will be performed where 50% of the subjects will be randomly assigned (balanced by Fitzpatrick skin type, separate randomization lists will be made for type I&II and types III-VI, at time of first visit subjects will be assigned to study or control group by giving them the next assignment on the appropriate list) to use the SHADE sensor and its app (study group), while the other 50% (control group) will receive standard of care UV counseling(placebo). Subjects will have 3 visits. The first and last visit will be standard of care visits at 0 month (enrollment), and the conclusion of their involvement. The second visit will be scheduled 3 months after the enrollment visit. The final visit will be scheduled as soon as practical, but at least 3 months after visit 2 and after September 30. On arrival at each visit, study personnel will pre-screen patients to ensure that the sensor is not visible to physician prior to examination, for example by placing it in their pocket. At each follow up visit, the number of actinic keratosis on the face and hands will be counted and photographed. They will be treated as per standard of care protocol with cryotherapy or curettage. General use of field therapies will not be permitted during the trial. Any lesions suspicious of non-melanoma or melanoma skin cancer will be photographed and biopsied as part of the standard of care algorithm. Cyclobutane pyrimidine dimers (CPD) levels will be measured by ELISA from exposed (cheek) and unexposed (buccal mucosa) skin scrapings collected at the first and last visit. For each patient, the CPD level from exposed skin will be normalized to the sun protected CPD level measured from unexposed skin. We will compare the normalized CPD level of control versus study participants at each timepoint and their average CPD change over time.

We will then compare these levels with Shade UV measurements. Finally, patients will also answer questions in PROMIS (Patient-Reported Outcomes Measurement Information System) in the fields of anxiety, depression and ability to participate socially to gauge their attitudes toward the sensor

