#### 10.4.2 ANALYSIS OF THE PRIMARY EFFICACY ENDPOINT(S)

##### **#1 (Primary): Quantify the impact of Shade on the cumulative number of new actinic keratoses developed over the study period.**

To test our primary aim, we will perform a control versus study group analysis. The study group will receive a Shade sensor and Shade app while the control group will standard of care sun avoidance counseling. The study will be randomized and single-blinded as described in section 10.6.1. This will also allow us to control for the effect of UV level variation on the primary outcome since the two groups will have balanced enrollment dates. All the patients will receive recommendations about UV exposure protection as defined by the recommendations of the American Academy of Dermatology and the National Cancer Institute.

Patients who will have used the Shade sensor for less than 15% of the days over the study period will be excluded from these analyses. We will use a Student's t-test with the following null and alternative hypothesis:

$$H_0: \text{mean}^C_{t12} (\text{AK}) = \text{mean}^I_{t12} (\text{AK})$$

$$H_a: \text{mean}^C_{t12} (\text{AK}) \neq \text{mean}^I_{t12} (\text{AK})$$

where  $\text{mean}^C_{t12} (\text{AK})$  is the averaged cumulative number of AK between enrollment follow up of controls and  $\text{mean}^I_{t12} (\text{AK})$  is the averaged cumulative number of AK of intervention patients.

In this analysis, demographic and clinical factors such as gender, age, baseline count of AKs, skin type, immunosuppressive treatment and comorbidity can be confounding factors. To test and control for confounding, demographic and clinical data (skin type, living area, gender, age, count of AK at enrollment, immunosuppressive (IS) treatment, level of immunosuppression and comorbidity) will be collected. We will use a stepwise multivariate approach with backward selection: 1) the effect of potential confounding factors will be tested using the same statistical tests, 2) factors with p-value <0.2 and less than 25% of missing values will be included in the multivariate model and 3) only covariates with significant adjusted p-value (<0.05) will be kept in the final model. Clinically relevant interactions will also be tested (e.g. skin type, gender, age) and kept in the final model if significant. The adjusted effect of Shade use will be estimated using a multivariate linear regression.

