**#6 (Secondary): Test the correlation between measured UV exposure and the number of new nonmelanoma skin cancers.**

We will test the correlation between the cumulative UV exposure and the number of new nonmelanoma skin cancers using a Pearson correlation test or a non-parametric Spearman test if the requirements for the parametric test are not met. A significant correlation will be defined as  $p > 0.2$  and  $p\text{-value} < 0.05$ . UV exposure will be defined as the cumulative UV exposure in erythemally-weighted  $\text{J/m}^2$  at each time point since enrollment.

**#7 (Secondary): Quantify the impact of Shade on keratinocyte DNA damage approximated by the measurement of cyclobutane pyrimidine dimers by ELISA.**

Cyclobutane Pyrimidine Dimers (CPD) are induced by UV exposure in a dose dependent fashion. UV exposure can lead to immediate CPD increase; therefore measurement of CPD following the delivery of a known UV dose allows for a biological readout of UV effects. In addition, CPD levels represent an equilibrium between UV induced formation and DNA repair; therefore, they can also reflect chronic UV exposure.

CPD level will be measured from ELISA from exposed (cheek) and unexposed (buccal mucosa) skin samples collected. For each patient, the level from exposed skin will be normalized to the basal CPD level measured from unexposed skin. Correlation of CPD level to Shade UV measurement 24 hours prior to collection will allow for an acute UV biological validation that Shade measured UV levels correspond to levels of CPD damage (using Pearson correlation test or a non-parametric Spearman test). We will also compare the normalized CPD level of control versus study participants at each timepoint and their average CPD change over time using a t-test. These comparisons will assess the accuracy of Shade measurements as it relates to chronic UV exposure.

The outcome will be a statistically significant reduction by at least 25% of the normalized CPD level of exposed keratinocytes.

**#8 (Secondary): Quantify the impact of Shade on patients' quality of life assessed by PROMIS (Patient-Reported Outcomes Measurement Information System) in the fields of anxiety (Mental Health), depression (Mental Health), and Ability to Participate in Social Roles and Activities (Social health).**

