We will also quantify the percentage of observant and non observant patients, as well as the percentage of responsive and non-responsive patients. While observance will be based on the use of the sensor, responsiveness will be based on "safe" UV behaviors. Observance will be defined as at least 50% of days used, poor observance between 15% to 50% and non-observance as inferior to 15%. Responsiveness will be defined as less than 15% days over the UV threshold and more than 85% of days with an UV threshold set within one standard deviation of the study group's average UV threshold. Conversely, non-responsiveness is defined as more than 15% days over the UV threshold or more than 85% of days with an UV threshold set above one standard deviation of the study group's average UV threshold.

The sociodemographic and clinical characteristics of observant, poorly observant, non-observant, responsive and non-responsive patients will be assessed separately and compared using Student's t-tests for quantitative characteristics and  $\chi^2$  for categorical characteristics. These comparisons will provide useful information to better understand the determinants of UV behaviour change.

To be conservative, only non-observant subjects (<15% of days use) will be excluded from the analyses while poorly and non-responsive patients will be included. The comparison of their characteristics will rule out a selection bias.

**#10 (Secondary): Assess feasibility of the intervention for kidney transplant recipients through report of their rates for compliance and retention.**

Rates will be reported but are not expected to be analyzed for significance.

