## 10.4.10 TABULATION OF INDIVIDUAL RESPONSE DATA

Clinical data tables will be reduced into a table of individual responses for analysis as follows:

Column	Source (name of CRF with data)
SubjectID	N/A
AK baseline (count)	Actinic Keratosis
AK follow up (cumulative count)	Actinic Keratosis
NMSC baseline (count)	NMSC
NMSC follow up (cumulative count)	NMSC
Observant % of days	Compliance database
Responsive Y/N	Shade database: days with UV limit below 90% of exposures
CPD R 0	Lab data
CPD R 12 month	Lab data
MHA 1	PROMIS MHA visit 1
MHA 2	PROMIS MHA visit 2
MHA 3	PROMIS MHA visit 3
MHD 1	PROMIS MHD
MHD 2	PROMIS MHD
MHD 3	PROMIS MHD
SHP 1	PROMIS SHP
SHP 2	PROMIS SHP
SHP 3	PROMIS SHP
UV Ave	Sensor data
AE (count)	CRF
comment	

group	Randomization
exclude	

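### Endpoint #5 correlates self-chosen UV exposure with new AKs without adjusting for the enrolment AK count or skin type, which dilutes the relation and leaves it open to confounding

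*Combined protocol and SAP*

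**What the plan says.** Section 10.4.3, #5: "We will test the correlation between the cumulative UV exposure and the number of AK lesions at each time point using a Pearson correlation test". Spearman's test is used if the parametric requirements fail. No covariate, stratification or partial correlation is named. Endpoint #6 has the same form for nonmelanoma skin cancers. The exposure is the cumulative erythemally weighted UV recorded by the device since enrolment.

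Section 2.2 states that the "control group will not wear a sensor", so only study-arm patients have a device reading. Under Section 4.1, "50% of the subjects will be randomly assigned" to the sensor out of 120 recruited. Section 10.4.3, #9 adds that "only non-observant subjects (<15% of days use) will be excluded from the analyses".

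For the primary comparison, Section 10.4.2 says that "demographic and clinical factors such as gender, age, baseline count of AKs, skin type, immunosuppressive treatment and comorbidity can be confounding factors" and handles them by backward selection. Endpoint #2 follows the primary procedure, and #3 and #4 repeat the stepwise adjustment. Endpoints #5 and #6 do not. The enrolment AK count is a column of the analysis table in Section 10.4.10, and Fitzpatrick type is determined at enrolment for randomisation (Sections 7.3.2 and 10.6.1).

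**The concern.** Endpoints #1 to #4 compare randomised arms, where chance and the skin-type lists already balance patient characteristics. Endpoint #5 relates lesions to an exposure that patients choose: under #9 they set their own daily limit and may exceed it. Randomisation protects nothing within one arm, yet this is where the plan drops the adjustment.

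Two things follow.

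- **Dilution.** Patients differ in underlying AK rate, and unexplained differences add noise. The plan itself assumes such differences: the simulation in Section 10.5 draws each patient's baseline rate from an observed distribution.
- **Confounding.** If AK propensity is related to current sun habits, the plain correlation is shifted. It moves upward if heavily exposed people also carry more past damage, and downward if AK-prone patients now avoid the sun, as all are counselled to do (Section 7.1.2).

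The Protocol Summary describes the study as communicating UV exposure and relating it to AK development. Endpoint #5 is the planned test of sensor readings against AKs. If it cannot separate current UV from prior propensity, neither a positive nor a null result is easy to interpret.

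**Working it through.** **Number of patients.** 120 × 50% = 60 sensor wearers, less those below 15% use (share not given). The scenarios below use 55 or 60.

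**What a plain correlation can detect.** At n = 60 the two-sided 5% critical value is r = t/√(n − 2 + t²) = 2.00/√(58 + 4.01) = 0.254. If the printed threshold of 0.2 refers to the coefficient, it never binds. By Fisher's z, power is Φ(atanh(ρ)·√57 − 1.96): 0.33 for ρ = 0.2, 0.65 for 0.3 and 0.79 for 0.35. Anything that lowers the attainable correlation therefore matters.

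**Spread of AK rates.** The documents give no mean or SD of AK counts, so the stated primary power of 0.81 (50 per arm, 25% reduction, Section 10.5) cannot be reproduced. It can be back-solved from δ/SD = (z_α + z_power)·√(2/50):

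- One-sided, as simulated in the plan: (1.645 + 0.878) × 0.2 = 0.505, so the CV of the total count is 0.25/0.505 ≈ 0.50.
- Two-sided: (1.960 + 0.878) × 0.2 = 0.568, so the CV is ≈ 0.44.

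Part of this is Poisson noise: rate CV = √(CV² − 1/mean). With an assumed mean of 8, √(0.44² − 0.125) ≈ 0.26. With a mean of 10, √(0.50² − 0.10) ≈ 0.39. A gamma-Poisson simulation of the primary t-test (one-sided, mean 8) gives power 0.83 at rate CV 0.4 and 0.74 at 0.5. If the stated power is trusted, the rate CV is probably about 0.3 to 0.45. A wider spread is possible.

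**Plain versus adjusted, scenario model (all inputs assumed).** Patient rates are log-normal, V1 and follow-up counts are Poisson, and UV acts on the log rate per SD. Tests are two-sided at 5%, counting significant results in the positive direction (nominal 2.5%). Spearman is compared with partial Spearman given the V1 count, n = 55, mean 4 to 10 new AKs:

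| Scenario | Rate CV | Plain | Adjusted |
|---|---|---|---|
| No UV effect, no link to propensity | 0.45-1.2 | 2-3% | 2-3% |
| UV effect 0.2, no link | 0.3-0.45 | 52-87% | 58-91% |
| UV effect 0.2, no link | 0.8-1.2 | 21-39% | 34-72% |
| No UV effect, link +0.3 | 0.3-1.2 | 17-51% | 10-16% |
| UV effect 0.3, link −0.3 | 0.8-1.2 | 3-12% | 30-82% |

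Pearson against partial Pearson at n = 60, mean 8, agrees in direction (plain/adjusted):

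| Rate CV | UV effect 0.2, no link | No UV effect, link +0.3 | UV effect 0.2, link −0.3 |
|---|---|---|---|
| 0.3 | 89/93% | 31/15% | 46/71% |
| 0.45 | 73/89% | 42/14% | 16/64% |
| 0.8 | 40/83% | 48/8% | 2/61% |
| 1.0 | 30/79% | 47/7% | 1/60% |

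These runs adjust for the V1 count only; skin type was not modelled.

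**The case against.** Several objections have force.

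- **Size.** A reader might infer that prior sun damage swamps the UV signal. The documents do not support that. At the spread implied by the stated power, the unconfounded loss is modest: with a mean of 10, about 86% plain against 90% adjusted at CV 0.3, and 75% against 86% at CV 0.4. Swamping needs a CV of about 0.8 or more, or AK-prone patients who now avoid the sun.
- **False positives.** A reader might call the 17-51% a false-positive rate. Endpoint #5 is worded as a test of correlation. If UV and propensity are related, UV and AK counts really are correlated, and rejecting zero is correct for that test. The result misleads only if it is read as the effect of current-season UV. The plan also treats AK number as reflecting UV effect, so the V1 count partly carries habitual exposure, and adjusting for it answers a narrower question. That is a reason to keep the plain correlation, not to report it alone.
- **Remedy.** One enrolment count is a noisy marker, so 10-16% remains against a nominal 2.5%. The count also depends on when the skin was last treated. With assumed extra V1 variation of CV 0.8 (propensity CV 0.8, mean 10), the adjusted figure rises to about 24-27%, and adjusted power for effect 0.2 falls from 72% to 52% (plain 41%). Adjustment still helps, but less.
- **UV measurement.** The model assumes perfect UV readings. Patients with use on as few as 15% of days stay in, so a cumulative total also reflects wear time. Both columns are optimistic, and adjustment does not address this.
- **Endpoint #6.** A reader might extend the point to #6. The form is the same, but no calculation supports a benefit from adjusting for the baseline skin-cancer count.
- **Importance.** #5 is one of nine secondary endpoints and drives no stated sample size or decision. #7 separately relates measured UV to CPD.

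**Conclusion.** The point holds as an omission that is nearly free to repair. The plan uses a bare two-variable correlation for its non-randomised exposure and leaves out the enrolment count and skin type that it names as possible confounders elsewhere. The direction is firm: in every scenario with a UV effect and no link, adjustment raises power; where UV and propensity are linked, it reduces the distortion; and with neither, both tests hold their nominal level.

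The size is uncertain, because it rests on an assumed AK mean, rate spread, UV effect and UV-propensity correlation. The documents give none of these directly. At spreads near those implied by the stated power, the unconfounded gain runs from a point or two to about 15 points of power; at wide spreads it is larger. The confounding risk is material across the whole range if a link of 0.3 exists, but no document shows that it does.

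**What to change.** In Section 10.4.3, #5:

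1. Pre-specify as the main analysis a partial Spearman correlation, or a log-link count regression such as negative binomial, of new AKs on cumulative UV. Adjust for the V1 AK count and the Fitzpatrick stratum, without stepwise selection.
2. Report the estimate with a 95% CI, and the unadjusted correlation beside it.
3. State that adjusting for one noisy enrolment count reduces confounding but does not remove it.
4. Align the outcome wording: the heading refers to new AKs, the method to the number of lesions.

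The same change in #6, with the baseline skin-cancer count, is optional.

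The cost is SAP wording and one or two degrees of freedom. Nothing new is collected. The table in Section 10.4.10 already holds the enrolment count, but it lists no skin-type column and gives UV as an average, so the stratum and the cumulative total should be added.

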**#6 (Secondary): Test the correlation between measured UV exposure and the number of new nonmelanoma skin cancers.**

We will test the correlation between the cumulative UV exposure and the number of new nonmelanoma skin cancers using a Pearson correlation test or a non-parametric Spearman test if the requirements for the parametric test are not met. A significant correlation will be defined as  $p > 0.2$  and  $p\text{-value} < 0.05$ . UV exposure will be defined as the cumulative UV exposure in erythemally-weighted  $\text{J/m}^2$  at each time point since enrollment.

**#7 (Secondary): Quantify the impact of Shade on keratinocyte DNA damage approximated by the measurement of cyclobutane pyrimidine dimers by ELISA.**

Cyclobutane Pyrimidine Dimers (CPD) are induced by UV exposure in a dose dependent fashion. UV exposure can lead to immediate CPD increase; therefore measurement of CPD following the delivery of a known UV dose allows for a biological readout of UV effects. In addition, CPD levels represent an equilibrium between UV induced formation and DNA repair; therefore, they can also reflect chronic UV exposure.

CPD level will be measured from ELISA from exposed (cheek) and unexposed (buccal mucosa) skin samples collected. For each patient, the level from exposed skin will be normalized to the basal CPD level measured from unexposed skin. Correlation of CPD level to Shade UV measurement 24 hours prior to collection will allow for an acute UV biological validation that Shade measured UV levels correspond to levels of CPD damage (using Pearson correlation test or a non-parametric Spearman test). We will also compare the normalized CPD level of control versus study participants at each timepoint and their average CPD change over time using a t-test. These comparisons will assess the accuracy of Shade measurements as it relates to chronic UV exposure.

The outcome will be a statistically significant reduction by at least 25% of the normalized CPD level of exposed keratinocytes.

**#8 (Secondary): Quantify the impact of Shade on patients' quality of life assessed by PROMIS (Patient-Reported Outcomes Measurement Information System) in the fields of anxiety (Mental Health), depression (Mental Health), and Ability to Participate in Social Roles and Activities (Social health).**

To assess the impact of Shade on quality of life, patients will be surveyed using short form paper versions of PROMIS (Patient-Reported Outcomes Measurement Information System) scores in the fields of depression, anxiety, and the ability to participate in social roles and activities. PROMIS survey will be performed at each visit. We will compare the change in PROMIS scores between group and study using a t-test at each time-point.

The outcome will be assessed for statistical significance (p-value of change in PROMIS score between groups) and clinical significance (changes of 3 points on a single score are generally considered meaningful to subjects).

**#9 (Secondary): Assess sensor usage in the study patient population and compare characteristics of observant vs non-observant and responsive vs non-responsive patients.**

To assess sensor usage, we will estimate the overall percentage (and 95% confidence interval) of days used in the study patient population, the average (and standard deviation) and median (and quartile) of the daily UV threshold set by the patients and the percentage of days below and above the UV threshold.

The Shade sensor and the mobile application enables users to decide, by looking at self-reported symptoms and daily cumulative UV exposure over 15 and 30 days, how much UV exposure in J/m^2 they would like to manage per day, which we call the daily UV threshold. Users can select a daily UV threshold that is lower than their previous maximum daily UV exposure. Of course, users are free to go beyond this threshold if they chose to and the app will let them know in real time by how much they have exceeded their threshold. The threshold can be adjusted at any time through the app. The Shade app does not make any recommendation regarding the daily threshold. Note that each subject will be individually counseled to minimize UV exposure.

We will also quantify the percentage of observant and non observant patients, as well as the percentage of responsive and non-responsive patients. While observance will be based on the use of the sensor, responsiveness will be based on "safe" UV behaviors. Observance will be defined as at least 50% of days used, poor observance between 15% to 50% and non-observance as inferior to 15%. Responsiveness will be defined as less than 15% days over the UV threshold and more than 85% of days with an UV threshold set within one standard deviation of the study group's average UV threshold. Conversely, non-responsiveness is defined as more than 15% days over the UV threshold or more than 85% of days with an UV threshold set above one standard deviation of the study group's average UV threshold.

The sociodemographic and clinical characteristics of observant, poorly observant, non-observant, responsive and non-responsive patients will be assessed separately and compared using Student's t-tests for quantitative characteristics and  $\chi^2$  for categorical characteristics. These comparisons will provide useful information to better understand the determinants of UV behaviour change.

To be conservative, only non-observant subjects (<15% of days use) will be excluded from the analyses while poorly and non-responsive patients will be included. The comparison of their characteristics will rule out a selection bias.

**#10 (Secondary): Assess feasibility of the intervention for kidney transplant recipients through report of their rates for compliance and retention.**

Rates will be reported but are not expected to be analyzed for significance.

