### 7.3.2 ENROLLMENT/BASELINE

During the enrollment visit the physician will complete a medical history including an assessment of Fitzpatrick skin type. The enrollment visit will include standard of care counseling on the importance of UV avoidance. For transplant recipients, condition appropriate information will be included.

Ultraviolet Exposure Counseling: as described in 7.1.2 Standard of Care Study Procedures

The enrollment visit will include the skin check described in 7.1.2 Standard of Care Study Procedures.

Skin Check: as described in 7.1.2 Standard of Care Study Procedures

Treatment of Actinic Keratoses as described in 7.1.2 Standard of Care Study Procedures.

At the conclusion of the enrollment visit the study coordinator will discuss with enrolling physician for determination of Fitzpatrick skin type. The coordinator will then assign the subject to treatment or control groups following the procedure in section [10.6.1](#). The subject's assignment will be noted on the randomization table to be kept confidential to the coordinator and study monitors.

The coordinator will meet with the subject in a separate room to schedule the first follow up visit. If the subject is in the treatment arm, in this meeting the subject will be given the box with the Shade sensor. The coordinator or a sponsor representative will observe and support the subject in the process of opening the box and installing the application on their phone. At this time the coordinator will assign a study email address to the subject and enter that address in the randomization table and an electronic table along with the subject's actual email address.

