### 10.6.1 ENROLLMENT/ RANDOMIZATION/ MASKING PROCEDURES

The randomization schedules will be developed prior to the enrollment of the first subject. There will be one schedule for Fitzpatrick types I-II and a second schedule for Fitzpatrick types III and higher. The randomization schedule is a simple list of assignments to the groups 'Treatment,' meaning that the subject will be given the Shade device and mobile application and 'Control,' meaning that the subjects will be given only the standard of care counseling to avoid UV. The following sequence of events at enrollment will ensure that the treating physician will be blinded to the subject assignment:

- (1) visit with study coordinator for screening, informed consent, and medical history.

If the subject passes screening and grants consent

- (2) physician visit.

During the physician visit, the study coordinator will take the next randomization from the randomization schedule. This schedule will be prepared by the sponsor in such a manner that the coordinator remains blind to the next assignment until it is requested. The sponsor has latitude to implement this using any reasonable physical or computational system. The subject assignment will be entered on the randomization schedule available only to the study coordinator and the study monitor.

- (3) wrap up conversation with study coordinator.

After the physician visit the study coordinator will sit with the subject in a separate room. The next visit or visits will be tentatively scheduled. If the subject is in the treatment group, the device will be provided and either the coordinator or a sponsor representative will work with the subject to setup the mobile application and ensure that subject understands how to use the device.

At subsequent visits subjects in the treatment group will be instructed to

- (1) avoid discussing their assignment with the physician.
- (2) place the shade sensor in a purse or pocket out of view of the physician
- (3) mention to the study coordinator if the subject of the assignment came up in conversation with the physician.

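### The between-arm CPD t-test can show the effect of having Shade, not the accuracy of its readings, because it uses no Shade reading

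*Combined protocol and SAP*

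**What the plan says.** Section 10.4.3, #7, has the heading aim of quantifying the impact of Shade on keratinocyte DNA damage. It plans two kinds of analysis.

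- A correlation within sensor wearers: "Correlation of CPD level to Shade UV measurement 24 hours prior to collection will allow for an acute UV biological validation".
- A between-arm t-test, introduced thus: "We will also compare the normalized CPD level of control versus study participants at each timepoint and their average CPD change over time using a" (the sentence closes by naming that test).

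Directly after the second it adds: "These comparisons will assess the accuracy of Shade measurements as it relates to chronic UV exposure". It then gives the success criterion for #7, a significant fall of 25% or more in normalised CPD.

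Other sections bear on this.

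- Section 2.2: the "control group will not wear a sensor". On the expected effect: "The behavior change in the treatment group is expected to be a result of both the decision to engage with the device", together with knowing one's own exposure.
- Section 10.6.1 defines control as "meaning that the subjects will be given only the standard of care counseling to avoid UV".
- Section 7.3.2, on the meeting that closes the enrolment visit: "If the subject is in the treatment arm, in this meeting the subject will be given the box with the Shade sensor".
- Section 4.1, after describing the CPD comparisons: "We will then compare these levels with Shade UV measurements". It gives no exposure window, test or criterion.

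**The concern.** The accuracy of a sensor is a relation between its readings and true exposure, or a marker of it, in the same person. A difference in mean CPD between arms is a different quantity. It reflects what people did with the device, and section 2.2 says as much. Reading one as the other can mislead in both directions: a good sensor that nobody heeds looks poor, and a poor sensor whose alerts keep people out of the sun looks good.

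The trial's title calls it a validation, and section 3 says its data will support the device's indications. A report that followed #7 as written would make a statement about measurement accuracy from a test that contains no measurement. The device-arm data that could address chronic exposure would have no specified analysis.

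**Working it through.** **Plan's own figure.** The documents give no power or precision for CPD or for sensor accuracy. The only power figure, 0.81 in section 10.5, is for AK counts and does not enter here.

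**Step 1. What enters the test.** Let Y be a patient's normalised CPD. The planned statistic is

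t = (mean Y in control − mean Y in study) / [s √(1/n_C + 1/n_S)].

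No term is a Shade reading. Accuracy can act on t only indirectly, through behaviour, and the test cannot separate the two. At visit 1 this is plain: the sensor is handed over after the physician visit, so the expected difference is zero by randomisation whatever the sensor's quality.

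**Step 2. Illustration.** Assumptions not in the documents: lognormal CPD with coefficient of variation (CV) 0.5, 60 per arm, and 4,000 simulated trials per row. Accuracy is expressed as rho, the correlation of log Shade dose with log CPD in the device arm.

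| True reduction in CPD | rho | Between-arm t-test significant | Device-arm Spearman significant and positive |
|---|---|---|---|
| none | 0 | 5.0% | 2.7% |
| none | 0.9 | 5.1% | 100% |
| 25% | 0 | 88.2% | 2.6% |
| 25% | 0.9 | 87.8% | 100% |

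The flat t-test column follows by construction from step 1; the simulation only puts numbers on it. With CV 1.0 and a 25% reduction, the t-test is significant in 19% to 37% of trials over 30 to 60 per arm, again regardless of rho.

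**Step 3. Which planned analyses pair CPD with Shade readings.**

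| Place | Pairing | Exposure window | Test |
|---|---|---|---|
| 10.4.3, #7, correlation | CPD with Shade UV | prior 24 hours, labelled acute | Pearson or Spearman |
| 10.4.3, #7, t-tests | none | none | t-test between arms |
| 4.1 | CPD with Shade UV | not stated | not stated |
| 10.4.3, #5 and #6 | Shade UV with lesions, not CPD | since enrolment | Pearson or Spearman |

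No CPD-to-Shade analysis for chronic exposure is specified. The ingredients exist: the table in section 10.4.10 has columns for average UV and for CPD.

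**Step 4. What a device-arm correlation could show.** Inputs: 120 patients allocated 1:1 (section 4.1), so at most 60 sensor users; two-sided 0.05 (section 10.4.1). CPD is collected at one site only (Protocol Summary; section 7.3.7) and that number is not given, so 30 is taken as an assumed lower case.

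Smallest significant correlation: r = t / √(n − 2 + t²).

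- n = 60: 2.002 / √(58 + 4.007) = 0.254.
- n = 30: 2.048 / √(28 + 4.196) = 0.361.

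True correlation needed for 80% power (Fisher z): r = tanh[(1.960 + 0.842) / √(n − 3)].

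- n = 60: tanh(2.802 / 7.550) = tanh(0.371) = 0.35.
- n = 30: tanh(2.802 / 5.196) = tanh(0.539) = 0.49.

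A true r of 0.25 at n = 60 would be significant only about half the time: atanh(0.25) × 7.550 = 1.928, and Φ(1.928 − 1.960) = 0.49. These are Pearson approximations. The simulated Spearman test gave about 60% at rho 0.3 with 60 users and about 33% with 30.

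**Step 5. Which visits have CPD.** Section 4.1 says first and last. The tube labels in section 7.2.3 allow visits 1, 2 and 3. The schedule in section 7.3.7 marks all three. Section 10.4.10 holds two values, at 0 and 12 months. Only the final visit is both supported by all four and preceded by sensor wear.

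**The case against.** The strongest reply is that one misworded sentence does little harm. Accuracy is neither an objective in section 3 nor a listed endpoint in section 4.2. The criterion for #7 is a reduction in CPD, and the between-arm t-test is the right analysis for that. No test, endpoint or sample size changes. All of this stands. A reader might infer that the trial is set up to pass a formal wrong verdict on the sensor, but the plan contains no accuracy threshold or decision rule, so the documents do not support that.

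A reader might also infer that CPD and chronic exposure are never to be compared. That goes too far: section 4.1 promises a comparison of CPD with Shade measurements and does not limit it to 24 hours. Underspecified is the fair word.

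Third, the sentence could be read as covering the 24-hour correlation as well as the t-tests. Even so, that correlation is acute by its own description and does not support a statement about chronic exposure.

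Finally, a correlation in the device arm is not proof of accuracy either. That is correct and limits what the repair may claim.

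**Conclusion.** The concern holds as a fault of interpretation together with an underspecified analysis. The inference in #7 from an arm difference to measurement accuracy is wrong as written. This needs no assumption: controls have no readings and the statistic uses none. The t-test itself is sound for the effect of the intervention on CPD and should stay.

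It is tempting to say that 60 users would detect a correlation of 0.25. That value is the threshold for significance, not an effect found with good power. For 80% power the true correlation must be about 0.35 with all 60 users and about 0.49 with an assumed 30. The simulated percentages rest on an assumed CV, distribution, subset size and rho; the conclusion does not depend on them. The point is worth correcting before analysis because the study is presented as a validation and the correction is cheap.

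**What to change.** 1. Delete the accuracy sentence in section 10.4.3, #7. Report the between-arm CPD comparison only as the effect of the intervention on CPD.
2. Make the comparison promised in section 4.1 concrete. Pre-specify, in the device arm, a rank correlation of normalised CPD at the final visit with Shade UV dose over a stated preceding window, with a stated way of accounting for days worn.
3. State whether the dose is taken before or after the app's reduction for logged sunscreen (section 6.1.2, Dashboard).
4. Include visit 2 only if sections 4.1, 7.2.3, 7.3.7 and 10.4.10 are reconciled to show that CPD is collected then.
5. Report the correlation with a confidence interval and describe it as an association, not as agreement in J/m² or as accuracy.

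The cost is SAP wording and one extra analysis of data the plan already collects at the final visit. That analysis may be imprecise in the one-site subset, and the SAP should say so.
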